Will Adult subjects who lack the capacity to give informed consent be enrolled in the research?

J7. Prisoners

Will Prisoners be enrolled in the research?

No

Section K: Research Related Health Information and Confidentiality

Will research data include identifiable subject information?

Yes

Information from health records such as diagnoses, progress notes, medications, lab or radiology findings, etc.

Yes

Specific information concerning alcohol abuse:

Yes

Specific information concerning drug abuse:

Yes

Specific information concerning sickle cell anemia:

No

Specific information concerning HIV:

No

Specific information concerning psychiatry notes:

No

Demographic information (name, D.O.B., age, gender, race, etc.):

Yes

Full Social Security #:

Yes

Partial Social Security # (Last four digits):

No

Billing or financial records:

Yes

Photographs, videotapes, and/or audiotapes of you:

Yes

Other:

No

At what institution will the physical research data be kept?

The physical research will be kept in our BCM offices housed in the [name].

Additionally the data will be stored in Redcap, a secure, online data base.

How will such physical research data be secured?

Data will be kept in locked file cabinets that only the research team has access to.

At what institution will the electronic research data be kept?

Electronic data will be kept on network computers in our BCM offices, under the password protected server. Address: \\discovery1.ad.bcm.edu\bcm-dept-icamp.

Data for this study may be stored electronically via RedCap in addition to physical storage. Electronic data will be stored using the REDCap (Research Electronic Data Capture) software. This software is used to electronically collect and manage research data. REDCap is a secure, web-based platform.

Such electronic research data will be secured via BCM IT Services- provided secured network storage of electronic research data (Non-Portable devices only):

Yes

Such electronic research data will be secured via Other:

No

Will there be anyone besides the PI, the study staff, the IRB and the sponsor, who will have access to identifiable research data?

No

Please describe the methods of transmission of any research data (including PHI, sensitive, and non-sensitive data) to sponsors and/or collaborators.

Transmissions, if any, will only happen via secure emails.

Will you obtain a Certificate of Confidentiality for this study?

No

Please further discuss any potential confidentiality issues related to this study.

NA

Section L: Cost/Payment

Delineate clinical procedures from research procedures. Will subject's insurance (or subject) be responsible for research related costs? If so state for which items subject's insurance (or subject) will be responsible (surgery, device, drugs, etc). If appropriate, discuss the availability of financial counseling.

Participating in this study will take the subject's time and will not involve any direct cost to him/her. The subject's medical insurance will be billed for all standard of care related expenses including:

¿ Wound care (CPT 97597), Post-op visit (99024) on visits 0, 2, and 4, ¿ Hba1c (CPT 83036) at visit 0 only if not previously available on EPIC

If subjects will be paid (money, gift certificates, coupons, etc.) to participate in this research project, please note the total dollar amount (or dollar value amount) and distribution plan (one payment, pro-rated payment, paid upon completion, etc) of the payment.

Dollar Amount:

450

Distribution Plan:

Subjects will be compensated \$75 per visit. We will be also providing parking validations. Visit 5 (Optional), in person visit compensation \$75. Remote visit compensation \$25.

Subjects will be given a ClinCard where payments will be loaded after a study visit is completed. Additional information will be provided to the subject about how to manage the card.

We will be requesting subjects SSN for payment purposes. This is required in order to provide them with a ClinCard.

Section M: Genetics

How would you classify your genetic study?

Discuss the potential for psychological, social, and/or physical harm subsequent to participation in this research. Please discuss, considering the following areas: risks to privacy, confidentiality, insurability, employability, immigration status, paternity status, educational opportunities, or social stigma.

Will subjects be offered any type of genetic education or counseling, and if so, who will provide the education or counseling and under what conditions will it be provided? If there is the possibility that a family's pedigree will be presented or published, please describe how you will protect family member's confidentiality?

Section N: Sample Collection

None

Section O: Drug Studies

Does the research involve the use of ANY drug* or biologic? (*A drug is defined as any substance that is used to elicit a pharmacologic or physiologic response whether it is for treatment or diagnostic purposes)

No

Does the research involve the use of ANY gene transfer agent for human gene transfer research? No

O1. Current Drugs

Is this study placebo-controlled?

No

Will the research involve a radioactive drug?

No

Section P: Device Studies

Does this research study involve the use of ANY device? Yes

Device 1: Transcu O2 device

Device 2: Sensilase

Device 3: Zephyr Bioharness

Device 4: Legsys

Device 5: Kent camera

Device 6: hyperview camera

Device 7: OxyGeni

Device 8: inSight

Section Q: Consent Form(s)

EO2 Concepts Study

Section R: Advertisements

None

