H1: OxyGeni oxygen delivery system will reduce the likelihood of surgical wound complication including tissue necrosis and its volume, infection, surgical revision, and amputation compare to standard of care dressing.

Aim2: To assess changes in skin perfusion in patients treated with OxyGeni oxygen delivery system.

H2: OxyGeni oxygen delivery system will improve perfusion in >50% of the patients as compared to baseline (measurements at baseline, 2 weeks, and 4 weeks).

Aim3: To evaluate changes in quality of life, anxiety during dressing change, and psychosocial parameters in patients with a surgical wound treated by OxyGeni oxygen delivery system

H3: Oxygen delivery will improve subject quality of life, reduce anxiety, and reduce perceived pain and physiological stress response during dressing change compared to the control group.

Aim4: To assess acceptability, user-friendliness, and Perception of benefit.

H4: OxyGeni oxygen delivery system will be considered to be practical to use, easy to use, and is perceived to be beneficial from both practitioner and subject as assessed by user friendliness questionnaire adapted for the purpose of this study (assessment at the conclusion of the study). This questionnaire is attached to the protocol.

H5. OxyGeni oxygen delivery system therapy will improve scar cosmetic appearance as assessed practitioner using the Scar Cosmesis Assessment and Rating (SCAR) Scale.

This is an exploratory study and our parameters of interest are: ¿ Complete wound healing post surgical intervention. ¿ % of wound complication post-surgical wound closure ¿ Perfusion improvement at 2 weeks, 4 weeks and 6 months compared to baseline and compared to the control group. ¿ Differences in pain, stress, anxiety, and quality of life compared to the control group ¿ Device acceptability and perception of benefit

Section E: Protocol Risks/Subjects

E1. Risk Category

Category 2: Research involving greater than minimal risk, but presenting the prospect of direct benefit to the individual subjects.

E2. Subjects

Gender:

Both

Age:

Adult (18-64 yrs), Geriatric (65+ yrs)

Ethnicity:

All Ethnicities

Primary Language:

English, Spanish

Groups to be recruited will include:

Patients

Which if any of the following vulnerable populations will be recruited as subjects?

Vulnerable populations require special protections. How will you obtain informed consent, protect subject confidentiality, and prevent undue coercion?

E3. Pregnant woman/fetus

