Will pregnant women and/or fetuses (as described in 45 CFR 46 Subpart B) be enrolled in the research? No

E4. Neonates

Will neonates of uncertain viability or nonviable neonates (as described in 45 CFR 46 Subpart B) be enrolled in the research?

E5. Children

Will children be enrolled in the research?

Section F: Design/Procedure

F1. Design

Select one category that most adequately describes your research:

c) Pilot

Discuss the research design including but not limited to such issues as: probability of group assignment, potential for subject to be randomized to placebo group, use of control subjects, etc.

This study will be a 4 weeks prospective (or up to wound healing or surgical revision, whichever came first), experimental study with N=60 consecutive patients, who are undergoing surgical closure.

Subjects will be randomized to either control or intervention group. The intervention group will receive the OxyGeni device and place the oxygen delivery within SOC dressing. The control group will receive standard of care wound dressing.

All patients will have baseline assessment including visual, dermal, neuropathy (Vibration Perception Threshold) and vascular assessment (ABI and Skin Perfusion Pressure). Then, the status of wound closure and presence of wound complication will be monitored every week. Each subjects will need up to 5 visits including baseline assessment, and weekly assessment up to 4 weeks or full wound healing or surgical revision, whichever came first, and an additional follow-up visit at a minimum 6 months after the surgery. At each visit, patients will be provided standard of care treatment including physical assessment, debridement and offloading. Table 1 in attachments' section summarizes the key measurement at each study visit.

Please note that no screening activities will take place prior to the patient signing a consent form.

Inclusion Criteria:

18-85 years of age. Ability to provide informed consent. Presence of a wound due to surgical intervention and closure. Subject or responsible caregiver is willing and able to maintain the required offloading (as applicable for the location of the wound) and applicable dressing changes

Exclusion Criteria:

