Charcot Arthropathy Bilateral AK/BK amputation Active Drug/alcohol abuse (or history of drug/alcohol abuse in last 1 month) Dementia or impaired cognitive function Subjects with osteomyelitis or extreme gangrene. Excessive lymphedema Presence of active infection Subject has a history of or any intercurrent illnesses or conditions that would compromise the safety of the subject according to judgement of a qualified wound specialist.

F2. Procedure

Please note that subjects will be consented before performing any study related measurements. This study will not bring any direct costs to the subject. The subject's medical insurance will be billed for all standard of care procedures.

Subjects who are randomized in the intervention group will receive the OxyGeni therapy into their SOC dressing. Those subjects allocated to the control group will only receive Standard of Care treatment. We will be reviewing the billing records for our patients to explore costs of both groups.

We may visit the patient's home for an appointment that doesn't require the physician present or to fix any issues with the device.

There will be a follow up phone call up to three months after the last visit. Additionally, there may be an optional six month follow-up that can be conducted remotely (via a video or phone call) or in-person. During the virtual six month follow-up the patient will be asked to answer questionnaires electronically via REDCAP. This will also involve uploading a photo of the neck area to allow for virtual assessment of scarring/wound healing. Finally, the subject will be asked to upload a video of them performing 20 seconds of elbow flexion-extension to allow for virtual frailty assessment. Should the subject be available for an in-person visit, questionnaires will be conducted in clinic. Upper-extremity frailty test will also be conducted in the clinic per description listed below. Digital images of the neck area and images using the Kent camera will be taken to assess scarring and tissue perfusion.

Study Tasks:

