Vascular Assessment: We will assess perfusion of the macro-circulation with arterial Doppler studies and micro-circulation with Skin Perfusion Pressure measurements and Ankle Brachial Index (ABI) will be measured on both extremities. Therefore, we will use the SensiLase system (Väsamed) to measure Skin Perfusion Pressure (SPP) in mmHg. The SensiLase is a device that will record the amount of Skin Perfusion Pressure. (Measurements will be done at screening/baseline visit and visits 2 & 4). We will also obtain oxygen tissue saturation images using Kent Camera or HyperView Camera (every visit)

-Ankle-Brachial Index: This test is to measure blood pressure of the ankle and arm while the subject is at rest. (Measurements will be done on screening/baseline visit and visits 2 & 4). Research Staff will: 1. Attach correct sized cuff on ankle and arm 2. Doppler probe will be placed on ankle and arm. 3. Cuffs will be inflated above your blood pressure. 4. The cuffs will deflate 5. Research Staff will document values in the subjects records. 6. Research Staff will remove the cuffs from the subjects ankle and arm.

-Skin Perfusion Pressure: This test will help the physician and researchers know if the tiny blood vessels in the subjects feet are blocked, damaged or if wound are getting enough blood to heal properly. (Measurements will be done on screening/baseline visit and visits 2 & 4) Research Staff will: 1. Ask the subject to lie flat 2. Research staff will place correct

sized pressure cuffs around the subjects ankles. 3. Research staff will also place an adhesive pad along with a sensor as (sensors will not be touching the skin directly) it will measure Skin Perfusion. 4. The cuffs will inflate above systolic blood pressure. 5. Research Staff will document values in the subjects record 6. Research Staff will remove cuffs from the ankle.

Adverse Event Reporting: Research Staff will document and report any study/non study related incident as per institution regulations. (Subjects will be asked on screening/baseline visit and visits 1- 4 and at the optional 5 visit).

Wound Assessment: A digital photo/video and thermal photo of wound will be taken for wound size verification and evaluate the area of inflammation. (Measurement will be performed at every visit). Photo may be taken with digital camera, KENT NIR camera, or eKARE camera.

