Pain Intensity Assessment (VAS): The subject will be provided with a numeric pain scale where he/she will report pain intensity. Research staff will document subject's pain level. (Measurements will be done at every visit)

WIFI wound classification (Wound, Ischemia, and foot infection): Podiatric (foot) physician will evaluate the health and wellness of the subject's feet in compliance of standard of care. (Will be done on screening/baseline visit and visit 4)

Screening/Baseline Visit *duration of visit 90 minutes This visit research staff will perform as described above: Medical History, Questionnaires (Pain, Social Factors, and Quality of Life, Sleep Quality, Cognitive Assessment, Frailty), Upper Extremity Test, Peripheral Neuropathy, Heart Rate Monitoring, Vascular Assessment, Wound Assessment, Wound Monitoring, Wifi Wound Classification, Dressing Change and Device Education.

Visit 1, One Week Later *duration 50 minutes This visit research staff will perform as described above: Pain Questionnaire, Heart Rate Monitoring, Adverse Event Reporting, Wound Assessment, Dressing Change and Device Education.

Visit 2, Two Weeks Later *duration of visit 80 minutes This visit research staff will perform as described above: Pain Questionnaire, Vascular Assessments, Heart Rate Monitoring, Adverse Event Reporting, Wound Monitoring, Wound Assessment, Dressing Change and Device Education.

Visit 3, Three Weeks Later *duration 60 minutes This visit research staff will perform as described above: Pain Questionnaire, Heart Rate Monitoring, Adverse Event Reporting, Wound Assessment, Dressing Change and Device Education.

Visit 4, Four Weeks Later *duration of visit 80 minutes This visit research staff will perform as described above: Questionnaires (Quality of Life, Acceptability, Pain, Frailty, Sleep Quality), Vascular Assessments, Heart Rate Monitoring, Adverse Event Reporting, Wound Monitoring, Wound Assessment, Dressing Change.

Visit 5, at a minimum of 6 months after surgery. This visit research staff will perform the SCAR assessment scale, POSAS,

and PASS questionnaires and take a digital picture of the scar. If the patient is unable to attend, the visit can be done remotely.

Section G: Sample Size/Data Analysis

G1. Sample Size

How many subjects (or specimens, or charts) will be used in this study?

Local: 60 Worldwide: 60

Please indicate why you chose the sample size proposed:

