This is a pilot study. We plan to recruit a convenient sample of 60subjects (30 subjects per group), which we anticipate to be sufficient to observe a trend between groups to examine proof of concept of EO2 OxyGeni oxygen to reduce the likelihood of wound complication post-surgical wound closure. Based on our initial prevalence chart review, we anticipate that 20-30% of patients in the control group will have failure in wound closure (e.g. necrosis, tissue necrosis and its volume, infection, surgical revision). We anticipate to reduce the incident of wound complication to less than 5%. Using a chi-square test and assuming an alpha level of 5%, and ratio risk reduction of 25%, we anticipate to have statistical power of 95% using a 30 sample per group.

Based on this pilot study, we will calculate power and will design a clinical trial accordingly.

G2. Data Analysis

Provide a description of your plan for data analysis. State the types of comparisons you plan (e.g. comparison of means, comparison of proportions, regressions, analysis of variance). Which is the PRIMARY comparison/analysis? How will the analyses proposed relate to the primary purposes of your study?

The primary outcome of this study is the percentage of wound complication incidents post surgical interventions. We will use chi-square to estimate whether the number of wound complication incidents is less in the intervention group compared to the control group. The secondary outcomes of this study are: improvement in skin perfusion and reduction in perceived pain, anxiety, and stress. We will use general linear model (GLM) univariate analysis (UNIANOVA) to examine significant difference between groups for the secondary parameters of interest. Results will be adjusted by demographic information (age, gender, BMI) and clinical information (size of initial wound, A1C level, baseline skin perfusion).

Section H: Potential Risks/Discomforts

H1. Potential Risks/Discomforts

Describe and assess any potential risks/discomforts; (physical, psychological, social, legal, or other) and assess the likelihood and seriousness of such risks:

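### H2 predicts perfusion improvement in more than half of OxyGeni patients against their own baseline, a mark that leaves out the control arm and has no matching analysis in G2

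*Combined protocol and SAP*

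**What the plan says.** Aim 2 in Section D concerns skin perfusion in patients treated with OxyGeni. Its hypothesis H2 reads "OxyGeni oxygen delivery system will improve perfusion in >50% of the patients as compared to baseline", with measurements at baseline, 2 weeks and 4 weeks. H2 names no comparator. H1 and H3, in the same section, do: one refers to standard-of-care dressing, the other to the control group.

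The parameters of interest that close Section D are framed differently. They include "Perfusion improvement at 2 weeks, 4 weeks and 6 months compared to baseline and compared to the control group".

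Section G2 lists improvement in skin perfusion as a secondary outcome and plans a general linear model "to examine significant difference between groups for the secondary parameters of interest". The adjustment covers age, gender, BMI and "clinical information (size of initial wound, A1C level, baseline skin perfusion"). G2 defines no perfusion responder and plans no test or interval for a proportion against 50%. Its chi-square test is assigned to wound complications.

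Under Vascular Assessment in F2, the SensiLase device will "record the amount of Skin Perfusion Pressure. (Measurements will be done at screening/baseline visit and visits 2 & 4"). Visits 2 and 4 fall at two and four weeks. F1 describes the study as "4 weeks prospective (or up to wound healing or surgical revision, whichever came first").

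**The concern.** A randomized trial has a control arm so that change over time can be compared with what happens without the intervention. H2 does not use it. After surgery, perfusion readings may rise or fall for reasons that have nothing to do with the device, and repeated readings vary by chance. A count of patients above their own baseline picks up all of this. H2 also sets no minimum change and does not say which of its two follow-up times counts.

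The stated hypothesis and the planned analysis therefore answer different questions. Someone reporting against H2 as worded could call Aim 2 supported while the G2 model shows no difference between arms. They could also call it unsupported when fewer than half improve on the device but fewer still improve on standard care.

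**Working it through.** **Plan's own figure.** There is none to reproduce. The documents give no perfusion mean, standard deviation, response rate, power or error rate for H2. The power statement in G1 concerns wound complications.

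**Text check.**

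| Place | Comparison for perfusion | Times |
|---|---|---|
| Section D, H2 | OxyGeni patients against own baseline, >50% improving | 2 and 4 weeks |
| Section D, parameter list | Against baseline and against control | 2 weeks, 4 weeks, 6 months |
| G2 | Between groups, adjusted for baseline skin perfusion | Not stated |

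H2 says only *the patients*. Reading this as the OxyGeni patients follows from Aim 2. On that reading, H2 is the only one of the three that leaves out the control arm, and nothing in G2 evaluates its >50% figure.

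**How the mark behaves with no device effect.** Inputs: 30 patients per arm (Section C background and G1). Assumptions: all 30 evaluable, one follow-up reading, no ties, patients independent, and the same chance *p* of a higher reading in both arms. The values of *p* are assumed.

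More than 50% of 30 means at least 16 patients. With X ~ Binomial(30, p), the probability of meeting the mark is

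P(X ≥ 16) = Σ from k = 16 to 30 of C(30, k) p^k (1 − p)^(30 − k).

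| Assumed p | P(mark met) | P(mark met and at least as many controls improve) |
|---|---|---|
| 0.40 | 0.097 | 0.006 |
| 0.50 | 0.428 | 0.112 |
| 0.60 | 0.825 | 0.388 |

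The p = 0.50 entry can be checked by symmetry: P(X = 15) = 0.1445, so P(X ≥ 16) = (1 − 0.1445)/2 = 0.428. The last column is P(X ≥ 16 and Y ≥ X), with Y an independent Binomial(30, p) for the control arm.

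**Sensitivity to loss of readings.** With an assumed 24 evaluable patients, 13 are needed. The probabilities are 0.114, 0.419 and 0.787 at p = 0.40, 0.50 and 0.60, so the picture does not change.

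**The opposite error.** If 45% improve on the device and fewer on standard care, the mark is missed with probability P(X ≤ 15) = 0.769, where X ~ Binomial(30, 0.45).

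**Would a formal one-arm test rescue the mark?** An exact one-sided 5% test against 50% needs 20 of 30, since P(X ≥ 20) = 0.0494 at p = 0.50 (19 of 30 gives 0.1002). That controls noise. If 60% improve in both arms, however, P(X ≥ 20) = 0.29, so shared change would still pass as a finding. Only the control arm addresses that.

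**The case against.** The strongest reply is that the plan already does what is asked. The Section D parameter list compares perfusion with control, and G2 supplies a baseline-adjusted between-group model. This stands, and it makes the point one of alignment: a single hypothesis sentence disagrees with the analysis around it. A reader might infer from H2 that the trial plans no control comparison for perfusion. The documents do not support that.

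Second, H2 is a predicted result in a study that calls itself exploratory. A reader might infer that 16 of 30 is a formal decision rule, or that the >50% result feeds the design of the later trial. No section says either. G1 says only that the pilot will be used to calculate power and design a trial, in a paragraph about wound complications. The probabilities above describe H2 if it is read as a success mark, and no more.

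Third, the rates are assumed and the answer moves from 10% to 82% with them. That is true. The spread shows that the result depends on a background rate that H2 ignores and the control arm would reveal. It does not predict what will happen in this trial.

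Fourth, the G2 model has weaknesses of its own. It adjusts for A1C, which F2 (Medical History) records only where the chart has it, while Section L provides for the test at visit 0 if it is not already available. Patients could drop out of the model if values are missing. This does not favour the >50% mark, but the number analysed should be reported.

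**Conclusion.** The concern holds as a minor one. H2 is framed within one arm of a randomized trial, its >50% figure has no analysis in G2, and as a success mark it cannot distinguish a device effect from noise or shared change. With 30 evaluable patients, no device effect and assumed improvement rates of 40%, 50% and 60%, it is met about 10%, 43% and 82% of the time. The conclusion that the mark and the analysis do not match rests on the text alone; only its size depends on the assumed rates. Severity is limited because perfusion is a secondary outcome in an exploratory pilot and the right comparison is already planned.

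Two neighbouring matters are separate and should be reconciled on their own. A reader might infer that the 6-month perfusion item in Section D has no measurement behind it. That goes too far: F2 says that at an in-person six-month visit "images using the Kent camera will be taken to assess scarring and tissue perfusion", and its Vascular Assessment text sets oxygen saturation images for every visit. The mismatch is partial. Skin Perfusion Pressure is not scheduled then, the remote option describes no perfusion measure, and the Visit 5 task list begins "This visit research staff will perform the SCAR assessment scale, POSAS" and names none. Table 1, an attachment, was not available to settle it. The other matter is whether patients with neck wounds, mentioned in F2, belong in a comparison of pressures taken with ankle cuffs.

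**What to change.** Restate H2 along these lines: skin perfusion at 2 weeks and at 4 weeks will be higher in the OxyGeni group than in the control group, adjusted for baseline skin perfusion. Test it with the between-group model already in G2, and report the adjusted difference with a 95% CI at both times. Making 4 weeks alone decisive is not advised without a stated reason, because follow-up can end earlier at healing or revision and the device may influence both.

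Drop >50% as a criterion. Show the percentage improving on baseline in both arms, as description only. Report by arm how many readings are missing at each time and why, and how many patients enter each model.

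The cost is a reworded hypothesis and a short table. No visit or measurement is added, since Skin Perfusion Pressure at baseline and at visits 2 and 4 is already scheduled. The downside is a slightly more demanding hypothesis. Counting the missing readings makes loss through early-ending follow-up visible but does not remove it.
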